The present study aims to compare the acute and training responses of (1) eccentric high intensity interval training, (2) work-matched continuous eccentric training, and (3) concentric high intensity interval training, all performed on cycle ergometers. The variables of interest include ratings of perceived exertion (RPE), cognitive demand (Fat), heart rate (HR), maximal oxygen consumption ($VO_{2\text{max}}$), maximal aerobic power (MAP), and various functional and health-related parameters.

It is hypothesized that eccentric HIIT will produce comparable or superior improvements in functional outcomes relative to concentric HIIT, but at a lower metabolic and perceptual cost. Furthermore, eccentric HIIT is expected to yield greater physiological benefits than continuous eccentric training for a similar perceived and metabolic load.

II. Population

A. Recruitment

The study was conducted on sedentary individuals aged 50–75, engaging in no more than 3 hours of light-to-moderate activity per week.

Participants were recruited through:

- Notices in the Movement Sciences Department (ULiège, Blanc-Gravier),
- Social media,
- Professional/personal networks.

All participants are legal adults, volunteers, and signed an informed consent form, previously approved by the University Hospital Ethics Committee of Liège (ref 2023/072).

B. Sample Size Estimation

Given the study design (three groups, two time points), a repeated-measures ANOVA was selected to assess within-group changes, between-group differences, and potential group \times time interactions. The primary outcomes were changes in isometric maximal strength and maximal aerobic power. The significance level (α) was set at 2.5% to account for multiple primary comparisons.

Assuming a moderate to large effect size ($f = 0.3\text{--}0.5$) and a statistical power of 80%, the required total sample size was estimated to range from $n = 18$ to $n = 36$. Accounting for an anticipated dropout rate of 20%, the recommended sample size ranged from 8 to 15 participants per group. Sample size calculations were performed using *G*Power* software.

Inclusion criteria:

- Aged 55 to 75 yo;
- Sedentary or engaging in <3h of regular physical activity/week.

Exclusion criteria:

- Smoking;
- Recent lower limb injury or pain (past 6 months) interfering with ergocycle tests;
- Uncontrolled acute or chronic disease;
- Cardiovascular disorders.

III. Experimental Protocol

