Aerobic endurance was evaluated via the 6MWT. Participants were instructed to walk as far as possible in six minutes along a 30-meter indoor track, turning around two cones at either end. HR and RPE were monitored throughout the test. The total distance covered was expressed in meters.

F. Statistical Analyses

All statistical analyses were conducted using R Commander (R version 4.4.2; R Foundation for Statistical Computing, Vienna, Austria). Data were initially assessed for normality using the Shapiro–Wilk test and for homogeneity of variances using Levene's test. For normally distributed variables with equal variances, repeated-measures analysis of variance (ANOVA) was used to examine the effects of time (pre- vs. post-intervention), group (EI, EC, CI), and their interaction. When significant main effects or interactions were found, post hoc comparisons were performed using Tukey's Honestly Significant Difference (HSD) test to control for Type I error.

For outcome variables related to participants characteristics and functional performance that did not meet the assumptions of normality, non-parametric tests were applied. Specifically, within-group comparisons across time were conducted using the Wilcoxon signed-rank test, and between-group comparisons were evaluated using the Kruskal–Wallis test.

All results were considered statistically significant at $p < 0.05$. Data are presented as mean \pm standard deviation (SD) for parametric variables and as median with interquartile range (IQR) for non-parametric variables, unless otherwise stated.

Summary

Phase 0 – Testing	Week –1 (2 sessions)	Evaluation
Phase 1 – Familiarization	Week 2-3 (2x/wk)	5' 20% MAP - 10' 30% MAP 15' 30% MAP - 20' 40% MAP 5' 20% - 10' 20% 15' 30% - 20' 30%
	Week 4-5 (EC, 2x/wk)	20' 40 et 50 % MAP, 60 rpm 30' 50 et 60% MAP, 60 rpm
	Week 4-5 (EI, 2x/wk)	6 x 2'-1' à 60 et 80% MAP, 60 rpm 9 x 2'-1' à 80 et 100% MAP, 60 rpm
	Week 4-5 (CI, 2x/wk)	6 x 2'-1' à 40 et 50% MAP, 60 rpm 9 x 2'-1' à 50 et 65% MAP, 60 rpm
Phase 2 – Training	Week 6-9 (EC, 3x/wk)	30' 80% MAP, 60 rpm
	Week 6-9 (EI, 3x/wk)	10 x 2'-1' 120% MAP, 60 rpm
	Week 6-9 (CI, 3x/wk)	10 x 2'-1' 80% MAP, 60 rpm
Phase 3 – Training	Week 10 – 13 (EC, 3x/wk)	30' 90% MAP, 60 rpm
	Week 10 – 13 (EI, 3x/wk)	10 x 2'-1' 135% MAP, 60 rpm
	Week 10 – 13 (CI, 3x/wk)	10 x 2'-1' 90% MAP, 60 rpm
Phase 4 – Retesting	Week 14	Evaluation

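### Sections II.B and III.F give different significance levels for the two primary outcomes; reconcile them, and write in a Holm step-down rather than a flat 2.5%

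*Combined protocol and SAP*

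**What the plan says.** Section II.B (Sample Size Estimation) defines two primary outcomes: "The primary outcomes were changes in isometric maximal strength and maximal aerobic power". It then lowers the significance level: "The significance level (α) was set at 2.5% to account for multiple primary comparisons". The method is not named, but 2.5% is 5% divided by two outcomes, which is a Bonferroni split. The sizing inputs are Cohen's f from 0.3 to 0.5, 80% power and a repeated-measures ANOVA with three groups and two time points. They lead to a total of 18 to 36, or 8 to 15 per group after 20% dropout.

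Section III.F (Statistical Analyses) does not carry the 2.5% forward. It states "All results were considered statistically significant at $p < 0.05". Its only multiplicity device is Tukey's HSD for post hoc comparisons, which does not act across the two primary outcomes. It does not say which ANOVA effect is primary. For non-normal variables it switches to Wilcoxon tests within groups and Kruskal–Wallis tests between groups. Neither section says whether one or both primary outcomes must succeed.

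**The concern.** There are two linked problems.

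First, the level used for sizing and the level written for analysis differ. If III.F is followed literally, the protection that II.B set out to provide is absent, and the chance of at least one false positive among the two primary outcomes is nearly doubled.

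Second, if the conflict is settled by copying a flat 2.5% into III.F, the plan adopts a rule that can be improved on for testing. Once the smaller p-value is at or below 0.025, the larger can be tested at 0.05 without exceeding 5% family-wise error, whatever the correlation between the outcomes. This is Holm's procedure. It rejects everything the flat split rejects and sometimes more. In a trial of this size, the difference in the chance of establishing both outcomes is worth having.

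**Working it through.** **Inputs.** From II.B: two primary outcomes, level 0.025, power 80%, f = 0.3 to 0.5, k = 3 groups, m = 2 time points, 20% dropout. Assumed, because the plan does not state them: pre-post correlation ρ = 0.5, equal group sizes, and the group × time interaction as the powered effect.

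**1. Reproduce the plan's sample sizes.** Noncentral F with λ = f²·N·m/(1 − ρ), df1 = (k − 1)(m − 1) = 2, df2 = (N − k)(m − 1) = N − 3, level 0.025, N in multiples of 3.
- f = 0.3, N = 36: λ = 0.09 × 36 × 2/0.5 = 12.96, df 2 and 33, power 80.3%.
- f = 0.5, N = 18: λ = 0.25 × 18 × 2/0.5 = 18, df 2 and 15, power 87.9%. N = 15 gives only 77.3%.
- Dropout: 36/0.8 = 45, or 15 per group; 18/0.8 = 22.5, or 7.5 per group, rounded up to 8.

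All the stated figures are recovered. The alternatives tried (within-subject or between-subject effect, λ = f²·N, levels of 0.05 and 0.0125) did not give both 18 and 36. So 2.5% is the level on which the trial was sized, and ρ = 0.5 for the interaction is a reasonable inference.

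**2. Power per test at the two levels** (p₁ at 0.025, p₂ at 0.05).
- f = 0.3, N = 36: p₁ = 0.8028, p₂ = 0.8779.
- f = 0.5, N = 18: p₁ = 0.8789, p₂ = 0.9378.

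**3. Chance that both outcomes are significant, if independent with equal f.** Flat 2.5%: p₁². Holm: p₂² − (p₂ − p₁)², that is, both at or below 0.05 except when both lie between 0.025 and 0.05. Unadjusted 5% each: p₂².

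| Scenario | Flat 2.5% | Holm | 5% each (III.F) |
|---|---|---|---|
| f = 0.3, N = 36 | 64.4% | 76.5% | 77.1% |
| f = 0.5, N = 18 | 77.2% | 87.6% | 87.9% |

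For the first row: 0.8028² = 0.644, and 0.8779² − 0.0751² = 0.765.

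**4. At least one success.** This is the same under flat 2.5% and Holm, because Holm's first step is also at 0.025: 1 − (1 − 0.8028)² = 96.1% at f = 0.3, N = 36.

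**5. Sensitivity of the gain, flat 2.5% to Holm.**
- Correlated outcomes, f = 0.3, N = 36 (60,000 simulated trials each): 66.6% to 77.4% at correlation 0.3; 68.6% to 78.6% at 0.5; 72.8% to 80.9% at 0.8.
- Unequal effects, f = 0.5 on one outcome and 0.3 on the other, independent: 80.2% to 87.8% at N = 36; 34.9% to 48.8% at N = 18.
- f = 0.5 on both at N = 36: power is already above 99%, so there is almost nothing to gain.

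**6. Family-wise error with no true effect.** Flat 2.5%: 1 − 0.975² = 4.94% if independent, at most 5% in general. Holm: at most 5%. 5% each: 1 − 0.95² = 9.75% if independent.

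**The case against.** The strongest objection is that the gain is measured against a rule the analysis section does not contain. The 2.5% stands only in II.B; III.F says 5%. Against III.F, Holm gives up a little power (76.5% against 77.1% for both). This is correct. A reader might infer from II.B alone that each outcome will be tested at 2.5% and that about 12 points of power are being lost. The documents do not establish that, because they contradict each other on the level. What remains is that the contradiction must be settled, and that Holm keeps almost all the power of 5% each while restoring the control that II.B intended.

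Second, the plan does not call the outcomes co-primary in the sense that both must succeed. If both were required, no split would be needed and each could be tested at 5%. If either is enough, Holm leaves the chance of at least one success unchanged. Both statements are true. Adjusting the level for multiplicity fits the reading that either outcome alone may support a claim. Under that reading, Holm's benefit is the second outcome.

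Third, a two-test Holm rule needs exactly one primary p-value per outcome. The plan does not name one, and its non-parametric branch has no interaction test. Isometric force is one of the functional tests in III.E, so that branch could apply to it. This stands and makes the fix longer than a single sentence.

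Fourth, Bonferroni is valid and simple and has matching simultaneous intervals, and the trial was sized to reach 80% at 2.5%. Also true: it would be wrong to infer that the trial is underpowered by its own assumptions or that a flat 2.5% is a validity error.

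**Conclusion.** The point holds in two parts. The conflict between II.B and III.F is in the text and bears on error control: 5% for each outcome gives 9.75% family-wise error if the outcomes are independent, against the 5% that II.B implies. The choice of Holm over a flat 2.5% is an efficiency improvement. It is worth about 7 to 14 percentage points in the chance that both outcomes are significant across the scenarios above, apart from the one where power is already above 99%.

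The result rests on the group × time test and ρ = 0.5, neither of which the plan states, although together they reproduce its sample sizes. The main figures also assume equal effects and independent outcomes; the gain shrinks to about 8 points at correlation 0.8 (f = 0.3, N = 36). That Holm never rejects less than the flat split, at the same 5% bound, depends on none of these assumptions.

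**What to change.** In III.F, state that:
- the primary test for each of the two primary outcomes is the between-group difference in change, that is, the group × time interaction or, if its assumptions fail, a Kruskal–Wallis test on the change scores;
- the smaller of the two primary p-values is tested at 0.025 and, if significant, the larger is tested at 0.05 (Holm);
- either outcome alone may support a claim, if that is the intention (if both are required, say so; no split is then needed);
- the p < 0.05 criterion applies only to the other outcomes.

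In II.B, keep 2.5% as the conservative level for sizing and refer to the rule in III.F.

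The cost is a few sentences and no participants. Confidence intervals that match Holm are less simple than Bonferroni intervals; unadjusted 95% or 97.5% intervals can be reported beside the tests, labelled as such. Much of the document is written in the past tense. If outcome data have already been seen, the change must be labelled post hoc.

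### On the reading that reproduces N = 18–36, the f = 0.3–0.5 called moderate to large is a between-arm difference in change of 1.27–1.47 SD (36 analysed) or 2.12–2.45 SD (18 analysed), so moderate between-arm effects are not powered

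*Combined protocol and SAP*

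**What the plan says.** Section II.B opens: "Given the study design (three groups, two time points), a repeated-measures ANOVA was selected", and gives the purpose as "to assess within-group changes, between-group differences, and potential group \times time interactions". On endpoints: "The primary outcomes were changes in isometric maximal strength and maximal aerobic power". Alpha "was set at 2.5% to account for multiple primary comparisons". The effect size is f = 0.3 to 0.5, introduced by "Assuming a moderate to large effect size", with "a statistical power of 80"%. From these, "the required total sample size was estimated to range from" 18 to 36, or 8 to 15 per group after 20% dropout, using G*Power.

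The section does not say which of the three listed effects f belongs to. It gives no pre/post correlation, no effect-size option, and no translation of f into Nm, watts or SDs.

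The hypotheses closing the Introduction are between-arm. Eccentric interval training (EI) is expected to do at least as well functionally as concentric interval training (CI), and to give more physiological benefit than continuous eccentric training (EC).

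**The concern.** When the primary outcomes are changes and the hypotheses compare arms, a reader will take a moderate effect to mean a moderate difference between arms in mean change. The value of f that G*Power accepts for a repeated-measures interaction need not be on that scale. With two time points it is converted to the change scale by a factor that depends on the pre/post correlation, so a label that suits the software input may not suit the difference in change.

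All three arms train actively, and one hypothesis allows EI and CI to be comparable. If the trial is thought to be powered for a moderate difference, a non-significant interaction could be taken as support for comparability. That would be unfounded if the test would usually miss such a difference.

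**Working it through.** **Inputs from section II.B:** k = 3 groups, m = 2 time points, alpha 0.025, power 80%, f = 0.3 and 0.5, dropout 20%. **Assumed, not stated:** equal allocation (N in multiples of 3), equal SD of change across arms, and, for reproducing N only, the group × time interaction with correlation ρ = 0.5.

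**1. Reproduce the plan's N.** For the interaction, λ = f²·N·m/(1−ρ), with df1 = (k−1)(m−1) = 2 and df2 = (N−k)(m−1) = N−3. At ρ = 0.5, λ = 4f²N.

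| f | N | λ | Power |
|---|---|---|---|
| 0.3 | 33 | 11.88 | 75.6% |
| 0.3 | 36 | 12.96 | 80.3% |
| 0.5 | 15 | 15.0 | 77.3% |
| 0.5 | 18 | 18.0 | 87.9% |

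The smallest adequate totals are 36 and 18, as stated. Dropout: 12/0.8 = 15 and 6/0.8 = 7.5, rounded up to 8 per group, also as stated.

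**2. Try other readings (alpha 0.025).**

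| Reading | N for f = 0.3 | N for f = 0.5 |
|---|---|---|
| Time main effect, ρ = 0.5 | 30 | 15 |
| Group main effect, ρ = 0.5 | 102 | 39 |
| One-way ANOVA on change scores | 132 | 51 |
| Interaction, ρ = 0.7 | 24 | 12 |
| Interaction, ρ = 0.8 | 18 | 12 |

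On a grid of ρ in steps of 0.01, the interaction gives 36 and 18 only for ρ from 0.50 to 0.52. The time effect gives them only at ρ = 0.37, and the group effect at no value.

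**3. Convert to the change scale.** With two time points, the interaction test is the one-way ANOVA on change scores, where λ = f_change²·N. Equating the two, f_change = f·√(2/(1−ρ)), which at ρ = 0.5 is 2f. So 0.3 becomes 0.6 and 0.5 becomes 1.0.

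**4. Express as the largest difference between arm means.** If one arm differs from two equal arms, d = f_change·3/√2. If the arms are evenly spread, d = f_change·√6.

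| f entered | f_change | One arm differs | Evenly spread |
|---|---|---|---|
| 0.3 | 0.6 | 1.27 SD | 1.47 SD |
| 0.5 | 1.0 | 2.12 SD | 2.45 SD |

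A simulation on change scores with 12 per arm gave 80% power for both patterns in the first row. With 6 per arm it gave 88% for both in the second.

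**5. Power if f = 0.3 or 0.5 is the between-arm difference in change itself.** Here λ = f_change²·N; for f_change = 0.3 and N = 36, λ = 0.09 × 36 = 3.24.

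| f_change | Largest difference | N = 18 | N = 36 | N = 45 |
|---|---|---|---|---|
| 0.3 | 0.64–0.73 SD | 10% | 22% | 29% |
| 0.5 | 1.06–1.22 SD | 27% | 62% | 75% |

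N = 45 is 15 per group with no dropout. At the 0.05 threshold in section III.F (Statistical Analyses), 36 analysed give 32% for f_change = 0.3.

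Steps 4 and 5 differ in what they assume. The link between the entered f and SDs of change needs ρ: the same f = 0.3–0.5 spans 1.08–2.07 SD at ρ = 0.3 and 2.01–3.87 SD at ρ = 0.8. The power for a given difference in SDs of change does not, because ρ drops out once the effect is on that scale.

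**The case against.** The strongest reply is that nothing has been miscalculated. On the most likely reading every stated figure is right, f is given numerically, and the moderate label belongs to f on the scale entered. This stands as far as it goes: a reader might infer an arithmetic error in N, and there is none on that reading. What remains is that the scale is undisclosed and is not that of the primary outcomes.

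Second, the interaction test and ρ = 0.5 are reverse-engineered; section II.B also lists within-group changes, and a time effect near ρ = 0.37 gives the same totals. This also stands, and the reading must be stated as an inference. The time-effect alternative would not help the between-arm hypotheses, which would then not have been sized at all.

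Third, a reader might infer that the trial is underpowered for its primary outcomes altogether. The documents do not support that. For the pre/post change pooled over arms (λ = d²N, df 1 and N−3, alpha 0.025), 36 analysed give 74% power for 0.5 SD of change and 89% for 0.6 SD. With 18 analysed these fall to 38% and 54%.

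Fourth, a reader might infer that 132 or 51 participants were required. Those totals follow only if f = 0.3–0.5 was meant as the between-arm difference in change, which the plan never says.

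Finally, what counts as moderate is a convention, and the plan sets no rule for interpreting a null result. Both are true. The check therefore takes the plan's own 0.3 as its benchmark, and the risk of misreading arises from the hypothesis that EI and CI may be comparable.

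**Conclusion.** The point holds for between-arm differences in change. With 36 analysed at alpha 0.025, the group × time test has 80% power only when the largest between-arm difference is 1.27 SD of change (one arm differs) or 1.47 SD (evenly spread). With 18 analysed it has 88% power for 2.12 or 2.45 SD. These are very large differences between active training arms. For a change-score f of 0.3, power is about 22% and 10%.

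These power figures rest on equal allocation, a common SD of change and alpha 0.025. Analysing all 45 recruits, or using 0.05 with 36, does not change the conclusion. That the plan's own f = 0.3–0.5 denotes these differences rests further on the inferred interaction test and ρ = 0.5, which the exact match of 36, 18, 15 and 8 supports but does not prove.

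**What to change.** In section II.B, replace the effect-size statement with wording such as:

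> With 36 participants analysed and alpha 0.025, the group × time test has 80% power for a largest between-arm difference in mean change of about 1.27–1.47 SD of change (with 18 analysed, 88% power for 2.12–2.45 SD). Power for 0.64–0.73 SD is about 22% (10% with 18).

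State which ANOVA effect, pre/post correlation and G*Power effect-size option produced 18–36. Drop the moderate label for the between-arm comparison. If the sponsor has SDs of change for the two primary outcomes, add the detectable differences in Nm and watts; the documents give no SDs from which to derive them.

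Add to section III.F that a non-significant interaction will not be read as showing that EI and CI are comparable.

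The cost is rewording and a less favourable stated figure. No further participants or measurements are needed.

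### The planned repeated-measures ANOVA compares unadjusted change scores; adjusting for baseline would gain power and remove bias from dropout that depends on baseline, but not from other dropout.

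*Combined protocol and SAP*

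**What the plan says.** Section II.B (Sample Size Estimation) fixes the outcomes and the model. "The primary outcomes were changes in isometric maximal strength and maximal aerobic power". "Given the study design (three groups, two time points), a repeated-measures ANOVA was selected to assess within-group changes, between-group differences", and the group by time interaction. "The significance level (α) was set at 2.5% to account for multiple primary comparisons". With 80% power and f from 0.3 to 0.5 the total is 18 to 36. It becomes 8 to 15 per group "Accounting for an anticipated dropout rate of 20" per cent. That is the only use the plan makes of the dropout figure.

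Section III.A gives one baseline assessment (week 1) and one post-intervention assessment (week 14).

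Section III.F (Statistical Analyses) repeats the model: "repeated-measures analysis of variance (ANOVA) was used to examine the effects of time (pre- vs. post-intervention), group (EI, EC, CI), and their interaction". For variables that fail the normality check, the arms are compared differently: "between-group comparisons were evaluated using the Kruskal–Wallis test". It does not say whether that test is applied to changes or to post values.

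The document names no baseline covariate, analysis set, missing-data rule or sensitivity analysis.

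**The concern.** With two time points, the group by time F test is identical to a one-way ANOVA of post minus pre. Two consequences follow.

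- **Precision.** A change score subtracts the whole baseline value, although post regresses on pre with a slope below 1 whenever the correlation is below 1 and the SDs are similar. The surplus baseline noise stays in the error term. With 8 to 15 per group that matters.
- **Bias.** A person without a week-14 value has no change score. If the less fit leave one arm more than another, that arm's remaining members start above average and regress towards the mean, so their average change is too low. The error works against the arm that lost its less fit members.

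Dropout could differ by arm. The Introduction says that interval eccentric work may at first cause more soreness and slower recovery than continuous work of the same load, and section III.C builds a familiarization phase to limit soreness, mainly in the eccentric groups. Both primary outcomes are changes, so the main comparison is the one exposed.

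**Working it through.** **Inputs from the plan:** three groups, two visits, alpha 0.025, power 80%, f = 0.3 to 0.5, dropout 20%, N = 18 to 36 in total, 8 to 15 per group.

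**Assumptions (not in the plan):** pre/post correlation ρ, equal SD of 1 at both visits, no true difference between arms, and the dropout mechanism.

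**1. The plan's own figures.** For the within-between interaction, λ = f²·N·2/(1−ρ) with (2, N−3) df. At ρ = 0.5:
- f = 0.3, N = 36: λ = 0.09×36×2/0.5 = 12.96, power 80.3%.
- f = 0.5, N = 18: λ = 0.25×18×2/0.5 = 18.0, power 87.9%.

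The required totals, in multiples of 3, are 36 and 18. Dividing 12 and 6 per group by 0.8 gives 15 and 7.5, rounded up to 8. Both stated ranges reproduce, so ρ = 0.5 is a reasonable reading of what was used.

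**2. Precision.** The variance of a change is 2(1−ρ). The variance of post given baseline is 1−ρ². Their ratio is (1+ρ)/2, which is 0.75 at ρ = 0.5. Dividing λ by 0.75 and giving up one error df:

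| N, f | λ, change | power | λ, adjusted | power |
|---|---|---|---|---|
| 36, 0.3 | 12.96 | 80% | 17.28 | 91% |
| 18, 0.5 | 18.0 | 88% | 24.0 | 95% |

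At ρ = 0.7 the gain at N = 36, f = 0.3 is smaller, 96.5% to 98.5%, because the ratio tends to 1 as ρ rises.

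**3. Bias if dropout depends on baseline.** Bias in an arm's mean change = −(1−ρ) × (mean baseline of those remaining, in SD above the full-arm mean).

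- *Split of 30%/20%/10%* (20% overall; logistic dropout, slope 1.5 per SD). The baseline means of those remaining rise by 0.327, 0.227 and 0.122 SD. The 30% arm against the 10% arm differs by 0.327 − 0.122 = 0.205. Multiplied by −(1−ρ), this gives −0.10, −0.06 and −0.02 at ρ = 0.5, 0.7 and 0.9. A split of 40% against 0% gives −0.21 at ρ = 0.5.
- *The 3 least fit of 15 leave one arm; losses elsewhere are unrelated to fitness.* The expected three lowest of 15 normal values are −1.736, −1.248 and −0.948, summing to −3.932. The 12 remaining average 3.932/12 = 0.328. The bias is −0.5×0.328 = −0.164 at ρ = 0.5 and −0.2×0.328 = −0.066 at ρ = 0.8. Simulation agrees (about −0.165 and −0.065).
- *Adjusted for baseline:* about 0.00 in both settings.
- *Equal 20% loss by the same mechanism in every arm:* no bias in either analysis.

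**4. What supplies the gain.** A mixed model with a common baseline mean on everyone randomised, and ANCOVA on people with both visits, gave the same two arm contrasts in a test dataset (−0.0958 and −0.0395 by both). With a single post visit, those without it add nothing to the contrast; the covariate does the work.

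**5. Bias if dropout depends on the unseen post value.**

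| Setting | ρ | unadjusted | adjusted |
|---|---|---|---|
| 30% v 10% | 0.5 | +0.10 | +0.16 |
| 30% v 10% | 0.7 | +0.06 | +0.11 |
| 30% v 10% | 0.9 | +0.02 | +0.05 |
| 3 lowest post of 15 leave one arm | 0.5 | +0.16 | +0.25 |

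Here adjustment does not remove the bias and makes it larger.

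**The case against.** The strongest reply is that no passage links dropout to baseline fitness. Soreness arises after randomisation. The Introduction says that gradual exposure attenuates it, and it expects lower effort and cardiovascular strain with eccentric intervals, so the concentric arm might equally lose more people. Section III.C sets loads as a percentage of each person's own maximal aerobic power, which weakens the idea that the less fit face a harder relative task. All of this stands: differential, baseline-related dropout is a possibility and not a forecast.

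The sizes are also modest. The three-least-fit case is close to the worst for a 20% loss in one arm. Even there, 0.165 is about 0.4 of the standard error of the arm contrast (0.40 in simulation at ρ = 0.5). If dropout follows some other measure only partly correlated with the outcome, the bias is about half as large or less, so the two primary outcomes need not be affected alike.

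A reader might infer that the plan prescribes a completers-only analysis. It does not; it is silent, and complete pairs are what the named method needs in practice. A reader might also infer that a mixed model on all randomised participants would cure the problem at no cost. Steps 4 and 5 show otherwise: inclusion of everyone is not the source of the gain, and the cure depends on dropout being explained by baseline.

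None of this touches the precision argument, which needs no dropout at all.

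**Conclusion.** The point holds in a limited form. The planned interaction test leaves a collected covariate unused. Under the correlation that reproduces the plan's own sample size, this costs about 11 points of power at N=36, f=0.3 and about 7 at N=18, f=0.5 (unrounded: 87.9% to 95.4%). The dropout bias is conditional: it needs loss that differs by arm, depends on baseline and occurs where ρ is below 1. It then lies between 0.02 and 0.10 SD in a moderate split and reaches roughly 0.165 baseline SD (ρ = 0.5) or 0.065 (ρ = 0.8) in the three-least-fit case. The documents give neither ρ, nor dropout by arm, nor a mechanism, so these are illustrations and not predictions. This is a worthwhile improvement to the plan and not a flaw that invalidates the trial.

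**What to change.** - In III.F, for both primary outcomes, compare the post value between assigned groups with the baseline value as covariate (ANCOVA). A mixed model with a common baseline mean is equivalent here, if small-sample inference is used.
- State the analysis set and how a missing week-14 value is handled.
- Report dropout and its reasons by arm.
- Add one missing-not-at-random sensitivity analysis, for example shifting the assumed post values of those who left, by arm, over a stated range.

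Cost: a few sentences, standard R functions and no new measurements. Statistically, it costs one error degree of freedom and the assumption of a common linear slope, which should be checked by plotting post against pre by arm. Much of the document is in the past tense; if the ANOVA has already been run, report the adjusted analysis beside it and label it as added later.
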